3.1.1 Estimands

The formal statistical analysis of primary, key secondary, and some supportive secondary endpoints consists of two strategies (hypothetical and treatment policy defined in Sections 3.1.1.2 and 3.1.1.3, respectively), supporting and supplementary analysis. Each strategy aims to answer a different clinical question of interest by using different ways to address intercurrent events. Definitions of relevant intercurrent events for this trial are provided in Section 3.1.1.1. Each strategy consists of a main approach and sensitivity analysis estimands. Different assumptions are made in each estimand analysis to predict the behaviour of the missing data so that predictions are aligned with the interpretation of the estimand. Sections 6.2.1 and 6.2.2 provide the handling of missing data for each estimand. Hypothetical strategy main analytical approach estimand is referred to as primary estimand, and treatment policy strategy main analytical estimand is referred to as secondary estimand.

The supportive analysis investigates alternative approaches regarding missing data. One supportive analyses are planned for this trial: tipping-point analysis described in Section 6.2.7.1. Two supplementary analyses for hypotetical strategy's main approach estimand are planned: ongoing asthma subgroup analysis described in Section 6.3.1.1 and patients from the same household described in Section 6.3.1.2.

3.1.1.1 Intercurrent events

IE are events occurring after treatment initiation that affect either the interpretation or the existence of the measurements associated with the clinical question of interest. It is necessary to address IEs when describing the clinical question of interest to precisely define the treatment effect that is to be estimated.

The IEs that have been identified as relevant is discontinuation of trial treatment. No additional IEs were identified during the conduct of the trial.

Due to the long duration of allergy immunotherapy, rescue medication is dispensed to every subject for ethical reasons. The use of rescue medication is, therefore, part of the treatment policy and as such, it is not classified as an intercurrent event for this trial.

3.1.1.2 Primary estimand

Primary estimand is referred to as the 'trial product estimand'. The trial product estimand assesses the anticipated effect of the 5-grass SLIT-drops if it is taken as instructed. This estimand is considered to be of most relevance to the patient population, as it describes the potential benefit they could obtain from the 5-grass SLIT-drops if they adhere to treatment for the planned duration. Adherence to treatment is considered important in immunotherapy since the optimal effect of immunotherapy is expected when taken consistently for a longer period.

Using the framework proposed in the ICH 2020, the trial product estimand can be described by:

- A. **Treatment:** 5-grass mix SLIT-drops, where rescue medication is taken as required
- B. **Population**: adults with grass pollen-induced rhinoconjunctivitis
- C. **Variables**: average daily allergic rhinoconjunctivitis TCS during 2nd PGPS
- D. **How to account for intercurrent events:** under the hypothetical situation where all subjects have completed treatment for the planned duration (hypothetical strategy).
- E. **Population summary**: absolute difference in means between treatment (see Section 9.5).

Statistical analysis plan	Date:	27-Oct-2023	A Lk
Trial ID: SU-G-01	Version:	1.0	
EudraCT No.: 2020-000455-12	Status:	Final	
CONFIDENTIAL	Page:	13 of 47	
	Page.	13 01 47	

A hypothetical strategy is used to address the intercurrent event of discontinuation of trial treatment. As such, if a subject discontinues trial treatment, only diary data up until the time of discontinuation is included in the analysis. Any diary data recorded after the discontinuation of trial treatment will be excluded from the analysis. Details of the handling of IEs for primary estimand main estimator are provided in section 6.2.1.

Put differently, the hypothetical assumption is that subjects remain on randomised treatment, but this does not necessarily imply that all subjects randomised to the same treatment experience similar benefits of that treatment. The determining factor is discontinuation of IMP due to following reasons (see section 6.1.2):

- due to "lack of efficacy"
- due to "IMP-related AEs"
- due to "other reasons"

Under the primary estimand, the assumption is that subjects who discontinue IMP due to "lack of efficacy" would not have experienced a treatment benefit other than that observed in the placebo arm. Contrary, subjects discontinuing for either of the two other reasons would have experienced a treatment benefit similar to the observed among subjects randomised to the same treatment arm.

These considerations imply that under the primary estimand, the only observed data used for analysis are obtained before discontinuation of IMP, while data obtained after discontinuation will be treated as missing. It further follows that imputation of missing data or data treated as missing will condition on the reason for discontinuation as outlined above. Moreover, data can be missing even for subjects not discontinuing IMP (e.g. due to low compliance). The reasoning for this type of missingness is ignorable and, consequently, this missing data will be imputed under the assumption that subjects experience a treatment benefit similar to that observed among subjects randomised to the same treatment arm. For further details, see section 6.2.1.

3.1.1.3 Secondary estimand

This estimand is referred to as the 'treatment policy estimand'. The treatment policy estimand assesses the treatment effect regardless of adherence to treatment and provides a broad perspective of the treatment effect in clinical practice in the expected population of patients. This estimand is in line with the 'intention to treat' principle and provides a robust assessment of the efficacy of the 5-grass SLIT-drops.

The treatment policy estimand can similarly to the trial product estimand be described by:

- A. **Treatment:** 5-grass mix SLIT-drops, where rescue medication is taken as required.
- B. Population: Adults with grass pollen-induced rhinoconjunctivitis
- C. Variable: average daily allergic rhinoconjunctivitis TCS during 2nd PGPS
- D. **How to account for intercurrent events:** regardless of whether subjects have complete treatment for the planned duration (treatment policy strategy).
- E. **Population summary**: absolute difference in means between treatment (see Section 9.5).

A treatment policy strategy is used to address the intercurrent event of discontinuation of trial treatment. As such, if a subject discontinues trial treatment, all available diary data will be included in the analysis, regardless of adherence to treatment. Details of the handling of IEs for secondary estimand main estimator are provided in section 6.2.2.

Statistical analysis plan	Date:	27-Oct-2023	ALK
Trial ID: SU-G-01	Version:	1.0	
EudraCT No.: 2020-000455-12	Status:	Final	
CONFIDENTIAL	Page:	14 of 47	

The secondary estimand's main feature is that subjects complete the trial though not necessarily, while still exposed to IMP. Therefore, all observed data is used in the analysis of this estimand irrespective of adherence to IMP, and only truly missing data needs to be imputed.

3.2 Study design

This is a phase III, randomised, parallel-group, double-blind, placebo-controlled trial of 5-grass mix SLIT-drops in adults with grass pollen-induced moderate to severe allergic rhinoconjunctivitis, with or without asthma. The trial was conducted over two grass pollen seasons.

A total of 440 adult subjects were planned to be randomised (1:1) to continuously receive either active treatment (grass SLIT-drops) or placebo treatment once daily

All subjects should receive daily treatment continuously from at least 16 weeks before the anticipated start of the 1st EGPS through the 2nd EGPS (definitions are provided in Section 9.1), corresponding to approximately 26 months of treatment (see Figure 1). Open-label rescue medication for AR/C was provided during the GPS. The subjects were asked to complete a RQLQ diary at V3 during the off-season for grass and tree pollen and then weekly during the EGPSs. The subjects were furthermore asked to fill in an eDiary daily during the EGPSs to capture information on rhinitis and/or conjunctivitis symptoms, use of symptom-relieving medications, and impact of rhinitis and/or conjunctivitis quality of life.

Figure 1 Trial design

Data for the primary endpoint were collected by the subjects by completing questions related to their daily symptoms and medication use in an electronic diary (eDiary).

No interim analysis was planned.

Routine safety surveillance was conducted throughout the trial. The follow-up visit was conducted via a telephone call approximately one week after the end of trial visit.

The first subject was randomised 15-Aug-2022 and subjects were planned to received treatment for 26 months. A total of 445 subjects were randomised and dosed.

Statistical analysis plan Trial ID: SU-G-01	Date: Version:	27-Oct-2023 1.0
EudraCT No.: 2020-000455-12	Status:	Final
CONFIDENTIAL	Page:	15 of 47

3.2.1 Flow chart

The flow chart can be found in protocol.

3.2.2 Actual trial timelines

The actual trial timelines are presented in Table 1.

Table 1 Trial timelines

First subject first visit (FSFV)	02-May-2021
Last subject randomised	31-Dec-2021
Last subject last visit (LSLV)	22-Sep-2023

3.2.3 Randomisation

The randomisation list was generated by a trial-independent statistician and will not be accessible to trial personnel involved in the conduct of the trial, until the database has been locked and all protocol deviations that have been identified, evaluated, classified, categorised and closed.

The randomisation was administered centrally via IRT and treatment allocation was stratified based on pre-existing diagnosis of asthma to ensure equal distribution of subjects with or without asthma across the treatments.

Randomisation errors

During the conduct of the trial, one randomisation error has occurred. An overview of the error can be found in supplementary document to the SAP: Documentation of Trial Analysis Sets. The randomisation error was included in the FAS. If missing data have occurred, it will be handled using the estimand framework.

4 Statistical hypotheses

4.1 Multiplicity adjustment

The trial product estimand is the primary estimand for all endpoints. The analyses for the primary and for the three key secondary endpoints will be controlled for multiplicity to ensure a family wise type I error rate is no larger than 5%.

The multiplicity will be controlled by employing a hierarchical testing procedure by prespecifying the order of the hypothesis to be tested. For the primary and key secondary endpoints the null hypothesis tested, is the hypothesis no difference between placebo and 5grass mix SLIT-drops treatment group.

The testing order of hypothesis is:

- 1. The primary efficacy analysis of the average daily allergic rhinoconjunctivitis TCS during the 2nd PGPS.
- 2. The key secondary efficacy analysis of average weekly overall RQLQ score during the 2nd PGPS.

Statistical analysis plan	Date:	27-Oct-2023	
Trial ID: SU-G-01	Version:	1.0	
EudraCT No.: 2020-000455-12	Status:	Final	
CONFIDENTIAL	Page:	16 of 47	

- 3. The key secondary efficacy analysis of average daily allergic rhinoconjunctivitis TCS during the 1st PGPS.
- 4. The key secondary efficacy analysis of average weekly overall RQLQ score during the 1st PGPS.

The primary endpoint is the 1st hypothesis in the hierarchy and will be tested on a 5% significance level. The testing of endpoints from the 2nd to the 4th in the hypothesis hierarchy will only be is only carried out formally if all previously tested hypotheses are statistically significant at the 5% level.

Additional endpoints and analyses are supportive in nature, thus they will not be controlled for multiplicity.

5 Analysis sets

5.1 Population sets

For the purposes of analyses, the following subject analysis sets are defined: TOS, FAS, SAF and AAS. The definitions are provided in Table 2.

Subject analysis sets	Description
Total Analysis Set (TOS)	All subjects who signed informed consent and thus includes screening failures.
Full Analysis Set (FAS)	FAS consists of all randomised subjects. Subjects are analysed as randomised i.e. according to their randomised assignment of treatment.
Safety Analysis Set (SAF)	SAF consists of all randomised subjects who received at least one dose of IMP. Subjects are analysed as treated i.e. according to treatment they actually received.
Asthma Analysis Set (AAS)	The AAS is a subgroup of the FAS and consists of subjects that have ongoing asthma at randomisation. Subjects are analysed as randomised i.e. according to their randomised assignment of treatment.

Table 2 Population sets

The TOS will be used for subject disposition output. The FAS will be used for baseline tables, all efficacy endpoints reporting; SAF will be used for safety data reporting; and AAS will be used for selected summary tables.

5.2 Data point sets

The following DPS are defined:

Table 3 Data point sets and observation periods.

DPS	Description
DPS1 (On-treatment observation period)	This includes all assessments that are observed while a subject is on treatment and within grass pollen season. For subjects who completed the trial, all assessments will be included, and for a subject that discontinued trial treatment, all assessments will be used until the treatment discontinuation.
	For relevant endpoints, baseline observation will also be included (
DPS2 (In-trial observation period)	This includes all assessments that are observed while a subject is in trial and within grass pollen season.
	For relevant endpoints, baseline observation will also be included (

FAS and DPS1 will be used to estimate the hypothetical strategy estimand, whereas FAS and DPS2 will be used to estimate the treatment policy estimand. Note that the on-treatment study period is only applicable for subjects exposed to randomised treatment.

6 Statistical analyses

Statistical analyses will be carried out by ALK, Biometrics, Hørsholm, Denmark. All computation will be performed using the statistical analysis system (SAS), SAS® version 9.4 or later.

The analyses described in this section along with the supporting information supplied in Section 9 specify the statistical analyses.

6.1 General considerations

The efficacy data will be analyzed using estimand framework. The primary and first key secondary endpoints will be analyzed based on on-treatment (DPS1) and in-trial (DPS2) data, while the rest of the endpoints will be analyzed based on on-treatment (DPS1) data. Different approaches of handling missing data will be applied. Overview of analysis methods and analysis sets to be used are summarized in **Error! Reference source not found.**

Table 4 Summary of analyses

Enapoint	Analysis methods	Analysis sets	Data type
	Trial product estimand – main approach		Imputed, DPS1
	Trial product estimand – sensitivity analysis		
	Treatment policy estimand – main approach		Imputed DBS2
	Treatment policy estimand – sensitivity analysis		
Primary endpoint:TCS during 2 nd PGPS	Supportive analysis: Tipping- point analysis under the trial estimand – main approach	FAS	
Key secondary enpoind: RQLQ during 2 nd PGPS	Supplementary analysis: Ongoing asthma subgroup analysis		Imputed, DPS1
	Supplementary analysis: Subjects from the same household		
	Supplementary analysis: Symptoms-score tertiles analysis		Observed, DPS1
	Descriptive analysis	FAS/AAS	
	Trial product estimand – main approach		Imputed DPS1
Key secondary enpoind:	Trial product estimand – sensitivity analysis		
TCS during 1 st EGPS RQLQ during 1 st EGPS	Treatment policy estimand – main approach	FAS	Imputed DPS1
	Treatment policy estimand – sensitivity analysis		
	Descriptive analysis		Observed, DPS1
Secondary endpoints:	Trial product estimand – main approach	FAS	Imputed, DPS1
	Descriptive analysis		Observed, DPS1
Secondary endpoints:	Descriptive analysis	SAF	Observed

Unless otherwise mentioned all the statistical tests described in this section will use a significance level of 5% and all tests and confidence intervals will be two-sided. All null hypotheses are "*no differences in means between treatment arms*" and the alternative hypotheses will always be "*a (not specified) difference*".

Descriptive statistics for efficacy endpoints will be based on observed on-treatment data. Descriptive statistics for numerical (continuous) variables include displaying treatment group mean, SD, median, minimum and maximum. Descriptive statistics for categorical variables will include frequency tables displaying the numbers and percentages.

Adjusted or "estimated" treatment group means (least squares means) will be estimated using coefficients across classification effects and, where relevant, continuous covariates proportional to those found in the relevant analysis set at baseline.

In addition to the inferential analyses, all efficacy endpoints will be presented in summary tables.

Where appropriate, summaries for the endpoints will be provided for 1st and 2nd seasons (eDiary data) and PGPS/EGPS, or by visits (vital signs, clinical laboratory assessments, physical examinations, and lung-function tests).

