2.6 Estimands for key secondary and supportive secondary objectives

The trial product estimand and treatment policy estimand, specified for the primary objective in Sections **2.4** and **2.5** respectively, are defined for each of the key secondary and supportive secondary objectives in a similar manner.

2.7 **Primary endpoint**

The primary efficacy endpoint is the average daily allergic rhinoconjunctivitis total combined score (TCS) during the 2nd PGPS.

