2.8.2 Supportive secondary endpoints

- The average weekly overall RQLQ score during the 1st EGPS.
- The average weekly overall RQLQ score during the 2nd EGPS.
- The average daily allergic rhinoconjunctivitis TCS during the 1st EGPS.
- The average daily allergic rhinoconjunctivitis TCS during the 2nd EGPS.
- The average daily allergic rhinoconjunctivitis DSS during the 1st PGPS.
- The average daily allergic rhinoconjunctivitis DSS during the 2nd PGPS.
- The average daily allergic rhinoconjunctivitis DSS during the 1st EGPS.
- The average daily allergic rhinoconjunctivitis DSS during the 2nd EGPS.
- The average daily allergic rhinoconjunctivitis DMS during the 1st PGPS.
- The average daily allergic rhinoconjunctivitis DMS during the 2nd PGPS.
- The average daily allergic rhinoconjunctivitis DMS during the 1st EGPS.
- The average daily allergic rhinoconjunctivitis DMS during the 2nd EGPS.

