15.1 Estimands

A primary and secondary estimand is defined for each of the primary, key secondary and supportive secondary objectives (see Sections 2.4 - 2.6 and 15.1.2 - 15.1.4) and a discussion of intercurrent events relevant for their definition is given in Section 15.1.1. The main estimator and sensitivity estimators for each estimand are defined in Section 15.11.1. Approaches for handling intercurrent events and missing data are given in Section 15.11.2, 15.11.3 and 15.14.

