15.11.4 Estimators for estimands defined for key secondary efficacy objectives

The key secondary and supportive secondary endpoints will be analysed identically to the primary endpoint using the definitions of the trial product estimand and treatment policy estimand (see Sections **2.4** and **2.5**) and the main and sensitivity estimators described in Section **15.11.1**.

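### SAP 6.1 and Table 4 give no supportive secondary endpoint a treatment policy analysis on in-trial data, although the protocol promises both estimands; SAP 3.1.1 conflicts and 6.5 does not list the change

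*SAP*

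**What the plan says.** **Protocol.** Section 15.1 states: "A primary and secondary estimand is defined for each of the primary, key secondary and supportive secondary objectives". Section 2.6 says the two estimands "are defined for each of the key secondary and supportive secondary objectives in a similar manner", and 15.1.4 repeats this, changing only the endpoint. Section 15.11.4 carries it into the analysis: the "supportive secondary endpoints will be analysed identically to the primary endpoint using the definitions of the trial product estimand and treatment policy estimand", with the main and sensitivity estimators of 15.11.1. Section 2.8.2 lists the endpoints concerned, starting with "The average weekly overall RQLQ score during the 1st EGPS".

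**SAP.**
- Section 3.1.1: "The formal statistical analysis of primary, key secondary, and some supportive secondary endpoints consists of two strategies". It does not say which supportive endpoints are meant.
- Section 5.2: "FAS and DPS2 will be used to estimate the treatment policy estimand".
- Section 6.1: the primary and first key secondary endpoints use both data sets, "while the rest of the endpoints will be analyzed based on on-treatment (DPS1) data".
- Table 4, first block (TCS and RQLQ, 2nd PGPS): both estimands, the treatment policy rows on in-trial data (printed DBS2, evidently DPS2).
- Table 4, second block (headed key secondary, naming TCS and RQLQ in the 1st EGPS): both estimands, but the treatment policy rows are on DPS1.
- Table 4, general secondary efficacy row on the FAS: the trial product main approach on imputed DPS1 data, plus descriptives.
- Section 6.5: seven changes from the protocol, none about estimands or estimators for supportive endpoints. Section 3 says that changes are documented there.

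**The concern.** The daily symptom score (DSS) and medication score (DMS) show whether a TCS effect comes from symptoms or from rescue medication. The EGPS averages show whether it holds over the whole season. Under SAP 6.1 these questions are answered only for the hypothetical case in which everyone stays on treatment, and diary data recorded after a subject stops IMP are set aside. SAP 3.1.1.3 itself describes the treatment policy estimand as the one that reflects clinical practice and follows the intention-to-treat principle.

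The second problem is disclosure. A reader who relies on 6.5 would conclude that Protocol 15.11.4 still stands. The programming team, working from 6.1 and Table 4, would produce something narrower.

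**Working it through.** **Nearby stated figure.** No power figure enters this point. The plan's 80% for TCS with 180 per arm reproduces: 1.64 / (5.5 × √(2/180)) = 2.829; 2.829 − 1.960 = 0.869; Φ(0.869) = 0.81. It is unaffected.

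**Count of endpoints (Protocol 2.8.2).** RQLQ EGPS, TCS EGPS, DSS PGPS, DSS EGPS, DMS PGPS and DMS EGPS, each in two seasons: 6 × 2 = 12. These six pairs are analyses 3 to 8 in Protocol Table 11. With one primary and three key secondary endpoints the total is 16.

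**What each SAP passage leaves.**

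| Source | Supportive endpoints with no treatment policy analysis |
|---|---|
| SAP 6.1 sentence | 12 of 12 (no DPS2 data) |
| Table 4 as printed | 10 of 12 have no treatment policy row; 12 of 12 have none on DPS2 |
| Table 4 with 1st EGPS read as 1st PGPS | 12 of 12 |
| SAP 3.1.1 | fewer than 12, number not stated |

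The 1st EGPS label in the second block is probably a slip. The block is headed key secondary, and Protocol 2.8.1, SAP 3.1 and SAP 4.1 all make the 1st PGPS the key secondary period. Even as printed, the rows rest on DPS1, which under SAP 5.2 serves the hypothetical estimand. The same 6.1 sentence also takes DPS2 away from two of the three key secondary endpoints (TCS and RQLQ, 1st PGPS).

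**Who would be handled differently.** The main imputation sources under the two estimands (SAP Tables 5 and 7) are:

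| Reason for stopping | Trial product | Treatment policy | Different? |
|---|---|---|---|
| Lack of efficacy | placebo | placebo | no |
| IMP-related AE, active arm | active | placebo | yes |
| IMP-related AE, placebo arm | placebo | placebo | no |
| Other reason, or data simply missing | own arm | own arm | no |

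Inputs (Protocol 15.2, conclusion): 10% discontinuation per year, 4.5% per year for adverse events, 220 per arm. Counting every AE discontinuation as IMP-related gives an upper bound:
- Season 1: 4.5% of the active arm; 0.045 × 220 = 9.9 subjects; 9.9 / 440 = 2.3% of all randomised.
- Season 2: 0.045 + 0.90 × 0.045 = 0.0855, about 8.6% of the active arm; 0.0855 × 220 = 18.8 subjects; 18.8 / 440 = 4.3% of all randomised.

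Subjects who stop IMP but go on with the diary are the other group affected: their later records count in DPS2 and not in DPS1. The documents give no rate for them, so the total share cannot be derived.

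**The case against.** The strongest defence is that little depends on this. The supportive endpoints carry no alpha (Protocol 15.10, SAP 4.1), both estimands remain for the primary and first key secondary endpoints, and the SAP says it was approved before lock and unblinding. Reporting supportive endpoints under one estimand is a defensible choice. All of that stands. It limits the weight of the point but does not answer the contradiction with Protocol 15.11.4 or the silence of 6.5.

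Three stronger readings are tempting, and the documents do not support them:
- A reader might infer a settled decision to drop the treatment policy estimand for all 12 endpoints. Only the 6.1 sentence says that. SAP 3.1.1 and the printed second block of Table 4 point the other way, and the available text of the general secondary row names no endpoints, so that row cannot settle it.
- A reader might take 10% in season 1 and 1 − 0.9² = 19% in season 2 as the share handled differently. Those are trial-discontinuation rates. Subjects who leave the trial have no later diary data to recover, and most are imputed by the same rule under both estimands.
- A reader might say that Protocol 5.1 obliges sites to collect these data. It asks for efforts, and for the primary and key secondary endpoints. Peak-season DSS and DMS come from the same diary records as TCS, but the section does not name the whole-season endpoints.

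**Conclusion.** The point holds as an undeclared and internally inconsistent narrowing of the protocol. SAP 6.1 and Table 4 together give none of the 12 supportive endpoints a treatment policy analysis on DPS2. For the general secondary row they also omit the protocol's sensitivity estimators. SAP 3.1.1 contradicts this without naming endpoints, the treatment policy rows in the second block of Table 4 contradict 5.2, and 6.5 is silent.

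The consequence is modest: the primary result, the testing order and the sample size do not change. The calculable part of the difference is at most 4.5% (season 1) and about 8.6% (season 2) of the active arm. This assumes the plan's discontinuation rates apply per year and equally by arm, and that every AE discontinuation is IMP-related. The part due to subjects who stop IMP but keep the diary is unknown.

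**What to change.** - In Table 4, add a row for the treatment policy main approach (FAS, DPS2) for the supportive endpoints, covering the six endpoint pairs, and amend the SAP 6.1 sentence to match.
- Reconcile 3.1.1, 5.2, 6.1 and Table 4. Name the supportive endpoints meant in 3.1.1, correct the 1st EGPS/1st PGPS label, and resolve the DPS1 entry against the treatment policy rows of the first-season key secondary endpoints.
- List any reduction that is kept, including the omitted sensitivity estimators, in 6.5 with a reason.

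The cost is a few more tables and some SAP wording. DPS2 and the imputation rules already exist, and no new data are needed. If the SAP can no longer be changed, the analysis is still prespecified in the protocol, and the departure from the SAP can be recorded in the clinical trial report, as Protocol 15 provides.

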Active	IMP-related AEs ^A	No	Placebo	No
Active	Other ^A	No	Active	No
Active	Data is missing ^B	No	Active	No
Placebo	Lack of efficacy ^A	Yes	Placebo	Yes
Placebo	IMP-related AEs ^A	Yes	Placebo	Yes
Placebo	Other ^A	Yes	Placebo	Yes
Placebo	Data is missing ^B	Yes	Placebo	Yes
Placebo	Lack of efficacy ^A	No	Placebo	No
Placebo	IMP-related AEs ^A	No	Placebo	No
Placebo	Other ^A	No	Placebo	No
Placebo	Data is missing ^B	No	Placebo	No

^A: Data is either (actually) missing or treated as missing because of "earlier" treatment discontinuation

^B: Data is missing prior to any observed date of treatment discontinuation

Otherwise, the sensitivity analyses will be similar to the main analyses.

6.2.3 Handling of intercurrent events and missing data for the treatment policy estimand – main approach

The relevant endpoints will be compared between treatment groups using the treatment policy estimand using FAS and DPS2. For subjects discontinuing trial treatment, all diary data (including data collected after discontinuation of trial treatment) will be included in the derivation of the relevant endpoint. Subjects for whom the primary endpoint is missing will be included in the analysis through multiple imputation as follows:

 For subjects discontinuing trial treatment due to IMP-related AEs or lack of efficacy, multiple imputation of the missing endpoint will be from the placebo group. This assumes that missing data following treatment-related discontinuation of trial treatment is MNAR

Statistical analysis plan	Date:	27-Oct-2023	
Trial ID: SU-G-01	Version:	1.0	
EudraCT No.: 2020-000455-12	Status:	Final	
CONFIDENTIAL	Page:	25 of 47	

and that subjects no longer taking active treatment for these reasons would have shown similar efficacy to subjects receiving placebo.

• For subjects discontinuing trial treatment due to other reasons than IMP-related AEs or lack of efficacy reasons or subject have missing data, multiple imputation of the missing endpoint will be taken from their own treatment group. This assumes that the missing data are MAR.

Otherwise, the analyses of the secondary estimand are similar to the main analyses of the primary estimand. The summary of missing data imputation is provided in Table 7

Table 7: Sources of	of observed	data used f	for imputation	under the	secondarv	estimand.
		aata aooa i	or impatation		oooonaary	ootinnania

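### SAP 6.1 and Table 4 give the 1st-season key secondary endpoints the wrong pollen window and give their treatment policy analysis on-treatment data, against the rest of the SAP and the protocol

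*SAP*

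**What the plan says.** SAP 6.1 assigns both on-treatment data (DPS1) and in-trial data (DPS2) to the primary and first key secondary endpoints, and then continues: "while the rest of the endpoints will be analyzed based on on-treatment (DPS1) data". In Table 4 the block for the remaining key secondaries is labelled "TCS during 1 st EGPS RQLQ during 1 st EGPS". That block lists the trial product and the treatment policy estimand, each with a main and a sensitivity analysis. The data type printed for the treatment policy rows is imputed DPS1. The matching cell in the block for the primary endpoint reads DBS2, evidently meant as DPS2.

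Elsewhere the SAP says something different. On the window, hypothesis 3 in SAP 4.1 is "The key secondary efficacy analysis of average daily allergic rhinoconjunctivitis TCS during the 1st PGPS", and hypothesis 4 is RQLQ in the same window. On the data, SAP 5.2 states the general rule: "FAS and DPS1 will be used to estimate the hypothetical strategy estimand, whereas FAS and DPS2 will be used to estimate the treatment policy estimand". For the treatment policy estimand, SAP 3.1.1.3 specifies that "all available diary data will be included in the analysis, regardless of adherence to treatment", and SAP 6.2.3 says "The relevant endpoints will be compared between treatment groups using the treatment policy estimand using FAS and DPS2".

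**The concern.** Table 4 is the SAP's overview of which analysis uses which data, so outputs may well be programmed from it. Two things would then go wrong.

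First, the rows for the 1st-season key secondaries would be run on the entire season. In protocol 2.8.2 and SAP 3.1 the 1st-season EGPS scores are supportive endpoints without multiplicity control. In SAP Appendix B each 2022 PGPS lasts 14 days, while the 2022 EGPS runs from 20 days (station CZUORL, 31 May to 19 June) to 110 days (station FRBRUL, 11 April to 29 July). An average over the EGPS is therefore a different endpoint.

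Second, DPS1 ends when a subject stops IMP. A treatment policy analysis on DPS1 discards the off-treatment diary data that protocol 5.1 asks sites to keep collecting. It would be another on-treatment analysis under a treatment policy label.

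**Working it through.** **1. Window for the 1st-season key secondaries**

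| Place | Window |
|---|---|
| Protocol 2.8.1 (key secondary endpoints) | 1st PGPS |
| Protocol 15.10 (hierarchy, items 3 and 4) | 1st PGPS |
| Protocol 15.11.1, Table 11 (analyses 1 and 2) | 1st PGPS |
| SAP 3.1 (endpoint list) | 1st PGPS |
| SAP 4.1 (hypotheses 3 and 4) | 1st PGPS |
| SAP Table 4 | 1st EGPS |

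Table 4 stands alone.

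**2. Data set for the treatment policy estimand**

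| Place | Data |
|---|---|
| SAP 3.1.1.3 | all available diary data |
| SAP 5.2 | FAS and DPS2 |
| SAP 6.2 | all observed data |
| SAP 6.2.3 | FAS and DPS2 |
| SAP 6.1 sentence | DPS1 for all but two endpoints |
| SAP Table 4, 1st-season key secondaries | imputed DPS1 |

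Protocol 15.11.4 requires the key secondaries to be analysed as the primary endpoint is, under both estimands. SAP 3.1.1 also applies both strategies to the key secondaries. SAP 6.5, which lists departures from the protocol, mentions neither the window nor the data set.

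**3. Consistency with the model.** Protocol Table 11 puts 1st- and 2nd-season PGPS scores into one repeated-measures model. SAP 6.2 and 9.5.2 keep a two-year model with treatment by year. Taken literally, Table 4 would need a treatment policy model with DPS2 in year 2 and DPS1 in year 1, and an EGPS year 1 paired with a PGPS year 2. Neither is specified anywhere.

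**4. Which tests are touched.** SAP 4.1 states: "The trial product estimand is the primary estimand for all endpoints". By SAP 5.2 that estimand uses DPS1. The confirmatory tests of hypotheses 3 and 4 therefore have the right data set. Only the treatment policy main and sensitivity analyses, which are outside the hierarchy, have the wrong one.

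**5. Size**

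Inputs from protocol 15.2 and SAP section 7: TCS difference 1.64, SD 5.5, 180 evaluable and 220 randomised per arm; 10% discontinuing per year, of whom 4.5 percentage points are for adverse events and 1 for lack of efficacy.

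- Check of the plan's own figure: the standard error is 5.5 × √(2/180) = 0.58. A two-sided 5% test with 180 per arm has power 80.75%, against 80% stated; 177 per arm would give 80%. This confirms the inputs; the point does not depend on it.
- Subjects discontinuing in a year: 0.10 × 220 = 22 per arm. This is the most whose 1st-season off-treatment data could be dropped; the range is 0 to 22.
- Share stopping for other reasons: 10% − 4.5% − 1% = 4.5%, or 0.045 × 220 = 9.9 per arm.
- Under the main treatment policy rules these subjects are imputed from their own arm. If active subjects in this group would in truth have shown no benefit off treatment, replacing their scores with active-arm values overstates the effect by 0.045 × 1.64 = 0.074, about 0.07 TCS. That is 4.5% of the effect and 0.074 / 0.58 = 0.13 of a standard error.

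This is a ceiling. It needs all of these subjects to stop IMP before the 1st PGPS, all to keep completing the diary, and none to retain any benefit. It also counts every adverse-event stop as IMP-related, because SAP 6.1.2 moves the others into the other-reasons group. Subjects stopping for IMP-related events or lack of efficacy are imputed from placebo, so they add no overstatement. The same holds for all stoppers in the treatment policy sensitivity analysis.

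**The case against.** A reader might infer that hypotheses 3 and 4 are set to be tested in the wrong window and on the wrong data. The documents do not support that. The hierarchy runs on the trial product estimand, for which DPS1 is correct, and every section that defines the hypotheses or endpoints says 1st PGPS. The joint two-season model also limits the risk: the PGPS models for TCS and RQLQ already yield the 1st-season contrasts, and running them on DPS2 for the 2nd-season endpoints gives the 1st-season treatment policy contrasts too. A programmer would have to leave that structure to produce the error. This stands, and it limits the point to a conflict between the overview and the definitions.

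A reader might also take 0.07 TCS as the expected bias. That does not stand either. Protocol 15.2 and SAP section 7 describe the 10% as discontinuing the trial. For subjects who stop IMP and leave together there is no later diary, and DPS1 and DPS2 coincide. A subject who stops during the peak keeps an observed average, as the second example in SAP 6.2.5 shows.

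Finally, the sentence in 6.1 does not itself say that treatment policy is run on DPS1. Read alone, it could mean that the other endpoints get only the trial product estimand. That is a fair reading, but it conflicts with the treatment policy rows in Table 4, with SAP 3.1.1 and with protocol 15.11.4, so a correction is needed either way. Table 4 has merged cells, so the pairing of rows and data types should be confirmed on the laid-out page. Its agreement with the 6.1 sentence makes a misreading unlikely.

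**Conclusion.** The contradiction is real and should be corrected. For the 1st-season key secondaries, Table 4 carries a window that belongs to supportive endpoints, and Table 4 and SAP 6.1 give a data set that does not fit the treatment policy estimand. Neither is declared as a change.

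The consequence is limited. The primary test, the type I error rate, the sample size and the hypotheses as worded in SAP 4.1 are unaffected. The data-set error reaches only treatment policy analyses outside the hierarchy. The window error would reach hypotheses 3 and 4 only if Table 4 were followed over SAP 4.1.

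The bias in the 1st-season treatment policy estimate cannot be derived, since the documents give no rate for subjects who stop IMP but continue the diary. For subjects stopping for other reasons, the plan's rates and the assumptions listed above put it between 0 and about 0.07 TCS.

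**What to change.** In Table 4, change both 1st-season key secondary labels to 1st PGPS, and set their treatment policy rows, main and sensitivity, to DPS2. In 6.1, state that the primary and all three key secondary endpoints are analysed on DPS1 for the trial product estimand and on DPS2 for the treatment policy estimand.

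If the treatment policy analysis was meant to be dropped for the 1st-season endpoints, delete those rows instead and record the departure from protocol 15.11.4, with its reason, in SAP 6.5. The label correction is needed in either case.

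The cost is one table and one sentence, plus an entry in 6.5 under the second option. The two-season models for the 2nd-season endpoints can be reused, and no sample size, alpha or power figure changes.
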